### **Risks/Benefits:**

Risks of study participation are the same as those for any standard fluoroscopically guided cervical ESI frequently performed in the PM&R Spine Clinic. These include: local infection, epidural hematoma or abscess, dural puncture and potential post-dural puncture headache, paresthesia during needle placement, pain at the injection side, failure of technique, allergy to latex or medications being used. Utilizing fluoroscopy, the risk of nerve damage, spinal cord injury or intravascular injection is less than 1:500,000. The length of stay and length of recovery is no longer than that of a standard ESI performed in the PM&R Spine Clinic at present.

There are no direct benefits to the individual by participating in this study. The patients will be presented with the same options of treatment whether they enroll in the study or decide not to. The information extracted from this study may provide the investigators a better understanding of patient's pain response following a cervical epidural steroid injection.

### **Study Termination Criteria**

- Adverse events considered/identified by the medical staff during the procedure process
- The subject requests to be withdrawn from the study during the procedure.

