### *Transforaminal epidural steroid injection*

After injection of 1 to 2 mL of 1% lidocaine to the skin and subcutaneous tissues, a 25-gauge spinal needle will be placed at the level and side of radicular pathology, based on clinical

correlation of symptoms/signs and magnetic resonance imaging findings. Advancement to the appropriate target position in the neuroforamen will be performed under fluoroscopic guidance according to practice guidelines. Once a satisfactory target position is achieved and confirmed in both anterior-posterior and oblique views, 0.5 to 1 mL of contrast (Omnipaque-240; GE Healthcare, Princeton, New Jersey) will be injected under live fluoroscopic observation with or without digital subtraction angiography depending on suggestion of vascular uptake, as is standard practice and recommended by practice guidelines. Upon confirmation of a satisfactory epidural contrast pattern without vascular uptake, the injectate will be delivered: dexamethasone sodium phosphate 1mL (10mg/mL) and 0.5 ml of 1% preservative-free lidocaine (total volume 1.5 mL). After the injection procedure, participants will be observed and then discharged from the clinic with written discharge instructions (current standard practice).

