#### *Repeat injections*

If a repeat injection is required, the patient will remain in the study. We will perform the same injection to which the patient was randomized for the first injection. We will document how many injections are required for patients to report at least 75% improvement in neck and arm pain. No more than 2 repeat injections will be performed during the study. This protocol was used in a previous study.

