#### **Data Collection:**

An electronic data collection sheet (via iPad) will be used to record all pre-procedure data (see data collection sheet):

- 1) Age (years).
- 2) Sex.
- 3) Height (cm).
- 4) Weight (Kg).
- 5) Duration of pain (weeks).

- 6) Location of cervical radicular pain based on clinical diagnosis: C2, C3, C4, C5, C6.
- 7) Radiologic diagnosis based on MRI of the Cervical Spine.

Before an initial injection, the following measures will be obtained:

- 7) NRS for pain; separate scores for neck pain and for arm pain
- 8) Neck Disability Index (NDI-5)
- 9) Medication Quantification Scale (MQS III) score
- 10) Daily opioid use in morphine equivalents

Immediately after injection the following will be obtained:

- 11) Fluoroscopy time
- 12) Post-injection NRS pain score; separate scores for neck pain and for arm pain
- 13) Adverse events, if they occurred

At intervals of 2 weeks, 1 month, 3 months, 6 months, and 1 year after injection, outcome measurements will be repeated. The Patient Global Impression of Change (PGIC) and a patient satisfaction score (five-point Likert scale: 1, very dissatisfied; 2, dissatisfied; 3, neither satisfied nor dissatisfied; 4, satisfied; and 5, very satisfied) will also be recorded. A single researcher blinded to group assignment collected all follow-up assessments in person, by e-mail, by telephone, or by mailed questionnaire.

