#### **Data Analysis Plan**

The primary outcome will be the proportion of participants with 50% or greater reduction in neck and arm pain on the NRS pain score at the 1-month follow-up assessment. Secondary outcomes included reduction in median NRS pain score (both neck pain and arm pain), NDI-5, MQS III, opioid consumption in daily morphine equivalents, PGIC score, and satisfaction score. Secondary outcomes will also be defined based on categorical “responder analysis” definitions of important clinical change given the National Institutes of Health recommendation for responder analysis in the assessment of therapeutic spine pain interventions. The responder analysis will include the proportion of patients with 30% or greater improvement on the NDI-5, a PGIC score less than 3 (indicating “improved” or “very much improved”), a 6.8 or greater point reduction on the MQS III score (equivalent to approximately 10 daily morphine equivalents), and the proportion of participants who undergo surgical spine surgery.

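### Adverse events are not named for recording at any of the five follow-up contacts, and the only stated later occasion for reviewing them is undefined; a secondary point is the unstated consequence of an adverse event during the procedure

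*Combined protocol and SAP*

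**What the plan says.** **Recording of adverse events.** In Data Collection, item 13, "Adverse events, if they occurred", stands in the list of items obtained immediately after injection. For later contacts the text reads "At intervals of 2 weeks, 1 month, 3 months, 6 months, and 1 year after injection, outcome measurements will be repeated". It then adds the global impression of change and the satisfaction score by name. Adverse events are not added. The contacts belong to one person: "A single researcher blinded to group assignment collected all follow-up assessments in person, by e-mail, by telephone, or by mailed questionnaire".

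**Discharge.** For the transforaminal arm, "participants will be observed and then discharged from the clinic with written discharge instructions", with no duration given. For the catheter arm the observation period is 20 to 30 minutes.

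**Later safety review.** The Safety Monitoring Plan commits its members to close contact throughout the study, in person and by telephone, and to reviewing adverse reactions with each subject. The stated occasions are delivery of the study drug and each collection of a sample. No sample collection is described anywhere in the protocol.

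**Termination.** Study Termination Criteria has two items: "Adverse events considered/identified by the medical staff during the procedure process" and "The subject requests to be withdrawn from the study during the procedure". The first states no consequence. Elsewhere, staying in the study is stated only for repeat treatment: "If a repeat injection is required, the patient will remain in the study". The primary outcome is a 50% or greater reduction in "neck and arm pain on the NRS pain score at the 1-month follow-up assessment".

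**The concern.** Risks/Benefits lists local infection, epidural hematoma or abscess, and post-dural puncture headache. These may appear only after the patient has gone home. If they are not asked about in the same way at fixed times, some will be volunteered and recorded and others will not. The trial compares a needle placed in the neuroforamen with a larger needle and catheter placed through C7-T1, so the harms may differ in kind and timing between arms. Uneven capture would weaken any comparison of harms between techniques, in a trial that is meant to inform the choice between them.

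The termination wording raises a smaller question. If an adverse event during the procedure ends participation, patients leave after randomisation and before the 1-month primary outcome, for a reason that may depend on the technique. Neither Data Analysis Plan nor Statistical analysis names an analysis population or says how missing outcomes are handled.

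**Working it through.** **1. Where adverse events are named for recording (Data Collection).**

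| Occasion | Adverse events named? |
|---|---|
| Immediately after injection | Yes (item 13) |
| 2 weeks | No |
| 1 month | No |
| 3 months | No |
| 6 months | No |
| 1 year | No |

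That is 0 of 5 follow-up contacts. Repeating the outcome measurements could be stretched to cover item 13, but Data Analysis Plan lists pain, disability, medication, opioid use, global impression, satisfaction and surgery as outcomes, and no adverse-event outcome.

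**2. Whether the Safety Monitoring Plan closes the gap.** It shows an intention to review adverse reactions after treatment. Its one later occasion, sample collection, corresponds to nothing in Procedures or Data Collection. The general promise of close contact names no times. The intention is there; the schedule is not.

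**3. What Study Termination Criteria settles.** The heading and the second item point towards leaving the study. Against that, both items are confined to the procedure, and the first refers to events that medical staff consider or identify, which can be read as a judgement about stopping the injection. The text does not decide between the two.

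**4. Illustration of the termination point.** The documents give no termination rate and no responder rate for the two arms. Every rate below is assumed, and losses are placed in one arm only unless stated.

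Let p be the true response, t the share lost from one arm, and r the response among those lost. Observed response in that arm = (p − t·r)/(1 − t). With p = 0.50:

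| t | r = 0 | r = 0.25 | r = 0.50 |
|---|---|---|---|
| 2% | 0.50/0.98 = 0.510 | 0.495/0.98 = 0.505 | 0.500 |
| 5% | 0.50/0.95 = 0.526 | 0.4875/0.95 = 0.513 | 0.500 |
| 10% | 0.50/0.90 = 0.556 | 0.475/0.90 = 0.528 | 0.500 |

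The false-positive rate is the exact binomial probability of rejecting at a two-sided 0.05 level (assumed) when the techniques do not differ. It starts from the planned 50 per group. Each cell gives the rate with no bias at the same group sizes, then the rate when all those lost are non-responders.

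| Lost | p | Chi-square (uncorrected) | Fisher |
|---|---|---|---|
| 1 of 50, one arm | 0.50 | 0.0450 to 0.0461 | 0.0439 to 0.0449 |
| 3 of 50, one arm | 0.50 | 0.0458 to 0.0572 | 0.0417 to 0.0512 |
| 5 of 50, one arm | 0.30 | 0.0486 to 0.0609 | 0.0385 to 0.0491 |
| 5 of 50, one arm | 0.50 | 0.0499 to 0.0855 | 0.0396 to 0.0679 |
| 5 of 50, one arm | 0.70 | 0.0486 to 0.1358 | 0.0385 to 0.1084 |
| 5 of 50, both arms | 0.50 | 0.0451 to 0.0458 | 0.0268 to 0.0277 |

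If a quarter of those lost would have responded, the 5-of-50, one-arm case at p = 0.50 reaches 0.0587 (chi-square) and 0.0465 (Fisher).

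**5. Size of the added work.** 5 contacts × 100 patients = 500 questions at most.

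**The case against.** Three objections deserve weight.

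*The Safety Monitoring Plan already provides for later review.* It does commit to that, so a reader who infers that no safety review is planned after discharge goes too far. The undefined term may have been meant as data collection, though the text does not say so. The data collection sheet is also not available to check. What stands is that the protocol text fixes no usable time for the review and no recording at the follow-up contacts.

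*No planned efficacy analysis depends on adverse events.* True: Data Analysis Plan names no adverse-event outcome. The matter is uniform capture of harms, not the validity of the primary comparison.

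*The termination wording is too thin a basis for a claim of bias.* This largely stands. A reader might infer that every procedural adverse event removes the patient and that the primary result is therefore biased. The documents do not say this. The item sets no such universal rule, and it may concern only the injection. Bias would need participation to end, the patients to be left out of the analysis, rates to differ by arm, and those patients to respond less often. None of the four is established, and equal loss in both arms changes almost nothing. The wider gap is the absence of any stated analysis population, including for the 20% attrition expected by 6 months; the termination wording is one narrow instance of it.

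**Conclusion.** The follow-up gap holds on the text alone and needs no assumed figures. Adverse events have one scheduled recording, immediately after injection, and none at the five later contacts; the stated later review has no defined occasion. The documents support saying that delayed harms may be captured unevenly. They do not show that harms will be missed, or missed more in one arm. This is worth correcting because the correction is cheap.

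The termination wording is a minor clarification. The text is silent on the consequence rather than wrong, and the calculations are illustration only. The largest figure, 0.136, requires 10% lost from one arm and none from the other, every one a non-responder, and 70% true response. At 1 of 50 lost there is practically no effect.

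**What to change.** 1. **Data Collection:** add one standard adverse-event question at each of the 2-week, 1-month, 3-month, 6-month and 1-year contacts, identical in both arms and placed after the outcome measures.
2. **Safety Monitoring Plan:** replace the reference to sample collection with those five contacts.
3. **Study Termination Criteria (minor):** separate stopping the injection from leaving the study, and leave the clinical decision to stop a procedure as it is. State that randomised patients keep scheduled follow-up unless they withdraw consent, and are analysed in their randomised group. State the same analysis rule in Statistical analysis.

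**Cost.** Amendment wording and at most 500 added questions at contacts already planned. Placing the question last protects the outcome answers at that contact only: an answer at 2 weeks could still reveal the arm to the single blinded researcher before the 1-month primary outcome. That risk is small but should be acknowledged. Having another existing team member ask would reduce it, but because the scheduled contacts belong to the blinded researcher and may be by e-mail or post, this could mean up to 500 separate contacts rather than 500 extra questions.

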### **Safety Monitoring Plan**

Safety will be monitored by all members of the study team:

[name]

[name]

The Principal Investigator is an MD at the University of Utah Orthopaedic Center. Members of the data and safety monitoring committee will be in close contact with all the subjects throughout the study, both in-person and via telephone. The members of the data and safety monitoring committee will review potential side effects and adverse reactions with each subject at the time of delivery of the study drug and at the time of each sample collection. All the committee members are located at the University of Utah Orthopaedic Center; all members have research experience.

